10.2.2.2 Safety variables

Safety variables will include AEs, laboratory changes (hematology, clinical chemistry and clinical urinalysis), abnormal findings in physical examination, changes in ECOG PS, changes in vital signs (weight, blood pressure, heart rate, respiratory rate, and body temperature), changes in ECG, changes in cardiac function test (EchoCG or MUGA scan) and changes in ophthalmologic examinations (visual acuity and slit lamp examination, IOP and Schirmer test if repeated). All AEs whether considered drug-related or not, will be reported on the CRF with a diagnosis, start/stop dates, action taken, whether treatment was discontinued, any corrective measures taken, outcome and other possible causes. For all events, the relationship to treatment and the intensity of the event according to CTCAE v4.03 will be determined by the investigator, using the terms and definitions given in Section 9.5.1.2.

Definition of treatment-emergent safety events

The treatment period for safety purposes is defined as the start of study treatment until 30 days after the last day of study treatment.

Treatment-emergent safety events (e.g. TEAEs) are safety events which arise or worsen during the treatment period.

Additional details will be described in the SAP.

Safety analysis

The final safety analysis will be performed at the time of the final primary endpoint analysis.. All enrolled patients who receive at least 1 dose of treatment will be valid for safety analysis. All observations pertinent to the safety of treatment will be recorded on the CRF and included in the Clinical Study Report (CSR).

Descriptive summary tables will be presented for all safety parameters. All TEAEs, treatment-emergent and hematological/biochemical toxicities based on laboratory measurements, as well as drug-related AEs and SAEs, will be graded by CTCAE v4.03 and categorized by MedDRA.

Results of physical examination, vital signs, ECG, and other safety variables as described in the SAP will be summarized. The number (%) of patients who discontinue study drug due to AE or for whom a dose reduction or interruption is needed due to AE will also be summarized.

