3.2 Rationale of the study

The need for new treatments for pancreatic cancer is great. At the MTD of 6.5 mg/kg Q3W, anetumab ravtansine has demonstrated a tolerable safety profile and efficacy in pancreatic cancer. If this study shows promise, with at least 21% of treated patients showing RECIST response, or prolonged delay in progression compared with historical controls, this would suggest the potential to impart large clinical benefit and warrant larger controlled trials.

4. Study objectives

The primary objective of this study is to:

- Test the activity/response rate per RECIST 1.1 criteria of anetumab ravtansine in patients with advanced pancreatic cancer who stain for mesothelin expression

The secondary objectives of this study are to:

- Time to Progression (TTP) defined as time from study treatment to RECIST 1.1 progression, or death (others going off study will be censored)
- Toxicity in pancreatic cancer patients (at 6.5 mg/kg dose)

5. Study design

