5.1 Design overview

This is a non-randomized, open-label, multicenter, Phase II study to evaluate the efficacy and safety of intravenous anetumab ravtansine (BAY 94-9343), an anti-mesothelin antibody drug conjugate, in pretreated mesothelin-expressing advanced pancreatic cancer.

At the time of the start of study treatment, the patients will have pretreated advanced pancreatic cancer that also overexpresses mesothelin as determined by immunohistochemistry (IHC). Mesothelin testing will be performed centrally.

A maximum of 30 patients will be enrolled in a minimax, Simon 2-stage design with a single early stopping rule for lack of efficacy. The target population is those patients with pancreatic cancer who have failed an earlier treatment. All patients will be treated with an anti-mesothelin immuno-conjugate, in this single arm, non-randomized trial and all patients treated with at least one dose of Anetumab will be included. The endpoint is any response using the RECIST 1.1 criteria.

The minimax, Simon 2-stage design testing 5% null hypothesis versus a 21% alternative requires a maximum of 30 patients. If there are no patients exhibiting any response among the first 20, which indicates a response rate less than 5%, then the trial will terminate early. If there is at least one response among the first 20 (indicating response rate of at least 5%) then the trial will accrue an additional 10 patients for a maximum of 30. Four or more responses out of 30 will reject the null hypothesis in favor of the 21% response alternative. These

criteria have significance level (alpha) 0.1 and power 90%. The probability of stopping early is 36% if the response rate is 5% or lower. The expected sample size is 26.4.

The start of the treatment period is defined by first administration of study drug (anetumab ravtansine). Patients will receive anetumab ravtansine IV infusion at a dose of 6.5 mg/kg (recommended Phase II dose [RPIID]) on Day 1 of a 21-day cycle. Treatment will be continued until death or occurrence of PD as defined by Response Evaluation Criteria in Solid Tumors (RECIST) v1.1 and assessed by blinded radiology review, or clinical progression, or until another criterion for withdrawal from the study is met.

Patients who discontinue study treatment for any reason other than confirmed radiological PD will be followed for progression during active follow-up (which includes the safety follow-up period) until confirmed PD for this patient is observed.

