All patients who end study treatment for any reason will be followed for OS and the start of any new anti-cancer treatment every 3 months during the long-term follow-up period until data maturation for the OS final analysis is reached, or until death, consent withdrawal or end of study, whichever occurs first.

Primary efficacy will be assessed based on radiological tumor evaluation by contrast-enhanced computed tomography (CT) or contrast-enhanced magnetic resonance imaging (MRI) of chest/abdomen/pelvis. During treatment as well as active follow-up, tumor imaging will be performed with the same modality to the extent possible, every 6 weeks during the first 6 months after the start of study treatment, every 9 weeks until the end of year 2, and every 12 weeks thereafter until RECIST confirmed radiological disease progression or end of study.

Safety evaluations will be done at full screening, at each clinic visit during the treatment period, and at the safety follow-up visit. The National Cancer Institute's Common Terminology Criteria for Adverse Events (NCI-CTCAE) version 4.03 will be used to grade severity of adverse events (AEs).

Patients will be contacted to assess survival status every 3 months during long-term follow-up. In addition, extra survival sweep contacts will be conducted at the time of PFS final analysis and prior to OS final analysis to ensure that long-term follow-up data is current.

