7.3 Dosage and administration

7.3.1 Administration of anetumab ravtansine

After reconstitution and dilution (as described in Section 7.2.1), anetumab ravtansine will be administered as a 1-hour IV infusion every 3 weeks on Day 1 of each 21-day cycle until confirmed radiological PD by RECIST 1.1, clinical progression as assessed by investigator, or any other criteria for withdrawal of treatment.

The individual dose will be 6.5 mg/kg per infusion from Cycle 1 onwards. In obese patients, anetumab ravtansine dose should be calculated considering a maximum weight of 100 kg.

Strict IV administration has to be ensured to avoid local intolerance reactions. After completion of the 1-hour anetumab ravtansine infusion, the infusion line will be rinsed with ≥ 100 mL of 0.9% saline solution to be administered as a short infusion.

See Section 9.1 for details on scheduled administrations.

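### The final safety analysis is tied to the primary endpoint analysis, with nothing to ensure that every patient's 30-day treatment-emergent window has closed by then and no later update planned

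*Combined protocol and SAP*

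**What the plan says.** The timing rule is in Section 10.2.2.2: "The final safety analysis will be performed at the time of the final primary endpoint analysis". That section also sets the period over which events count: "The treatment period for safety purposes is defined as the start of study treatment until 30 days after the last day of study treatment". The safety set is every treated patient: "All enrolled patients who receive at least 1 dose of treatment will be valid for safety analysis". The planned tables include the number and percentage of patients who discontinue, reduce or interrupt the drug because of an adverse event.

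Treatment has no fixed end. Section 7.3.1 continues it "until confirmed radiological PD by RECIST 1.1, clinical progression as assessed by investigator, or any other criteria for withdrawal of treatment", and Section 5.1 plans imaging "every 6 weeks during the first 6 months after the start of study treatment, every 9 weeks until the end of year 2", then at 12-week intervals. Section 9.2.5.1 already schedules a safety visit 30 (±7) days after the last dose.

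Toxicity is one of the two secondary objectives in Section 4. The early-stopping rule in Section 5.1 is: "If there are no patients exhibiting any response among the first 20, which indicates a response rate less than 5%, then the trial will terminate" (that is, before the second stage). Section 10.3 describes the look at 20 patients as an interim analysis of response rate.

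**The concern.** A response rate is settled by response assessments, with scans every 6 weeks at first. It can be known while some patients are still being dosed or are within 30 days of their last dose. A safety analysis labelled final and run at that moment would leave those patients' windows open. They would be a mix of recent enrollees and patients on drug for a long time because of response or stable disease.

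The counts at risk are those that can only rise with further dosing and follow-up: patients with a given adverse event, a dose reduction or a discontinuation. Section 3.1 shows that these are not rare. In the 6.5 mg/kg expansion cohort, 16 of 32 patients needed a dose reduction and 12 of 32 had corneal toxicity. In a table of 30 patients, each patient reclassified is worth 1/30 = 3.3 percentage points; in a table of 20, it is 5 points.

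**Working it through.** **The plan's own figures.** None is stated for the safety timing. The design figures that bear on it reproduce. The chance of stopping at 0/20 when the response rate is 5% is 0.95^20 = 0.358 (stated 36%). The expected sample size is 20 + 10 × (1 − 0.358) = 26.4 (stated 26.4). An early stop is therefore a realistic route to the final analysis if the drug is inactive.

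**Assumed inputs (none is in the documents).**
- Entry is uniform over A = 12 to 24 months.
- Time on treatment is exponential with median m = 2 to 4 months, so λ = ln 2 / m.
- The data cutoff falls c after the last entry. Twelve weeks is 12 × 12/52 = 2.77 months.
- The 30-day window is taken as 1 month.

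**Open windows at the cutoff.** A patient followed for t months has an open window with probability exp(−λ(t − 1)). The last patient has t = c. The other 29 have t spread uniformly from c to c + E, where E = A × 30/31 is the expected span of entries. With S = exp(−λ(c − 1)), the expected number open is S + 29 × S × (1 − exp(−λE)) / (λE).

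- Low end (m = 2, A = 24): λ = 0.347, S = 0.542, λE = 8.05. Result: 0.542 + 29 × 0.0673 = 2.5.
- High end (m = 4, A = 12): λ = 0.173, S = 0.736, λE = 2.01. Result: 0.736 + 29 × 0.317 = 9.9.

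Simulation of the same model agrees (2.5 to 9.9). A later cutoff multiplies each result by exp(−λ × delay):
- 18 weeks (1.385 months later): 2.5 × 0.62 = 1.5, and 9.9 × 0.79 = 7.8.
- 26 weeks (3.23 months later): 2.5 × 0.33 = 0.8, and 9.9 × 0.57 = 5.7.

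A second set of assumptions (median 6 to 18 weeks, accrual 52 to 104 weeks, evenly spaced entries) gives 1.2 to 9.7 at 12 weeks and 0.2 to 5.7 at 26 weeks. If the cutoff is at least 30 days after every patient's last dose, the number is 0.

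**After a stop at 20.** At the same accrual rate (8 to 16 months for 20 patients), with 19 and 20/21 in place of 29 and 30/31, the 12-week figures are 2.5 to 8.5 open windows.

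**From open windows to missed events.** A patient with an open window may already have had the event, so open windows overstate the loss. As an illustration, assume a constant event hazard h over treatment plus 1 month. Choose h so that 37.5% (12/32) or 50% (16/32) of patients are eventually affected: 1 − exp(−h) × λ/(λ + h) = 0.375 or 0.50. The chance that a patient followed for t months has a first event after the cutoff is exp(−ht) × exp(−λ(t − 1)) × h/(λ + h). Averaged over the 30 patients at 12 weeks:
- Smallest (m = 2, A = 24, 50%, h = 0.214): 0.114 for the last patient and 0.0088 on average for the rest. (0.114 + 29 × 0.0088)/30 = 1.2 percentage points.
- Largest (m = 4, A = 12, 50%, h = 0.131): 0.220 and 0.0606. (0.220 + 29 × 0.0606)/30 = 6.6 percentage points.

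At later cutoffs the largest shortfall comes from the 37.5% case (h = 0.082), which starts at 6.4 points. At 18 weeks it is 6.4 × exp(−0.2555 × 1.385) = 4.5; at 26 weeks it is 6.4 × exp(−0.2555 × 3.23) = 2.8. For scale, the 95% half-width for 37.5% of 30 patients is 1.96 × √(0.375 × 0.625/30) = 17 points. A hazard that rises with cumulative exposure would give a larger shortfall.

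**The case against.** The strongest reply is that truncation is not established. The protocol gives no data cutoff for the primary analysis. It also describes the primary variable in conflicting ways: response rate in Section 5.2, progression-free survival in Section 9.4, and a time to progression or death in Section 10.2.2. Under the last two, the final primary analysis could fall after most patients have stopped treatment. This stands, and it makes the loss possible rather than certain. It does not remove the gap: Section 10.2.2 censors patients without an event, so even that analysis does not require everyone to be off drug.

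Second, the same paragraph promises: "All observations pertinent to the safety of treatment will be recorded on the CRF and included in the Clinical Study Report (CSR"). Late events would therefore be recorded and reported somewhere. This is a real mitigation, but it sets no cutoff and does not say that the final tables will be re-run.

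Third, the safety analysis is descriptive, with no test or decision rule attached, and the monitoring committee reviews the study at least every six months (Section 13.2). Both lower the severity. Committee review is oversight, however, not the reported answer to the toxicity objective. Section 10.2.2.2 leaves further detail to the SAP, but it states the timing itself.

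A reader might infer three stronger things that the documents do not support:
- That patients will certainly be cut off. With no stated cutoff, this cannot be shown.
- That the loss falls only on the longest-exposed patients. Those with open windows would include recent enrollees.
- That the final safety tables are locked at the look at 20 patients. Section 10.3 calls that look an interim analysis of response rate, and nothing says when data are cut after an early stop.

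**Conclusion.** The point holds as a gap in the timing rule. The plan labels a safety analysis final without ensuring that the data it summarizes are complete, and it schedules no update. If the primary analysis comes soon after the last response assessments, or soon after a stop at 0/20, the final tables can understate rates of treatment-emergent events, dose reductions and discontinuations.

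The size cannot be read from the documents. It rests wholly on assumed accrual, treatment duration and cutoff, and under the constant-hazard illustration the bias is smaller than the sampling error of a 30-patient table. Data are complete for patients more than 30 days past their last dose; only the tail of exposure in the others is at risk. Sample size, alpha and power are unaffected. This is a cheap improvement of low severity.

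**What to change.** Replace the timing sentence in Section 10.2.2.2 with:

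*Safety will be summarized at the primary response analysis; the final safety analysis will be performed after the last treated patient has completed the 30-day safety follow-up visit (or died, withdrawn consent or been lost to follow-up).*

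State that the same rule applies if the trial stops at 20 patients.

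The change uses a visit already scheduled in Section 9.2.5.1 and adds no patients or procedures. The cost is a second run of the tables, and final toxicity tables that come later than the response result. Because treatment is open-ended, one patient on drug for a long time could hold the final tables open; the response result and the first safety summary need not wait.

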10.2.3 Other variables

10.2.3.1 Biomarker variables

An analysis of mesothelin expression levels in all patients evaluated for mesothelin expression will be performed. Biomarker parameters that may predict response, e.g. mesothelin expression levels in tumors and in plasma, may be analyzed by patient, and associated with tumor response using descriptive statistics, if appropriate. The association between biomarker and selected safety, efficacy, or PK parameters may be graphically displayed. Further exploratory statistical analyses may be performed. Biomarker variables and analyses will be further described in the SAP.

10.3 Planned interim analyses

An interim analysis for RR at the time 20 patients are evaluable will be performed.

11. Data handling and quality assurance

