	
Patients will be treated and undergo imaging scan every 6 weeks.
 
RECIST 1.1 criteria to be used for response
 
Descriptive statistics of RR (response rate) + 95% CI
 
Time to Progression calculated by K-M method
 
All patients treated with at least one dose of Anetumab to be included
 
A maximum of 30 patients will be enrolled in a minimax, Simon 2-stage design with a single early stopping rule for lack of efficacy. The target population is those patients with pancreatic cancer who have failed an earlier treatment. All patients will be treated with an anti-mesothelin immuno-conjugate, in this single arm, non-randomized trial. The endpoint is any response using the RECIST 1.1 criteria.
 
The minimax, Simon 2-stage design testing 5% null hypothesis versus a 21% alternative requires a maximum of 30 patients. If there are no patients exhibiting any response among the first 20, which indicates a response rate less than 5%, then the trial will terminate early. If there is at least one response among the first 20 (indicating response rate of at least 5%), then the trial will accrue an additional 10 patients for a maximum of 30. Four or more responses out of 30 will reject the null hypothesis in favor of the 21% response alternative. These criteria have significance level (alpha) 0.1 and power 90%. The probability of stopping early is 36% if the response rate is 5% or lower. The expected sample size is 26.4.

Methodology	
Primary efficacy will be assessed based on radiological tumor evaluation by contrast-enhanced computed tomography (CT) or contrast-enhanced magnetic resonance imaging (MRI) of chest/abdomen/pelvis. During treatment as well as active follow-up, tumor imaging will be performed with the same modality to the extent possible, every 6 weeks during the first 6 months after the start of study treatment, every 9 weeks until the end of year 2, and every 12 weeks thereafter until RECIST confirmed radiological disease progression or end of study.
 
Safety evaluations will be done at full screening, at each clinic visit during the treatment period, and at the safety follow-up visit. The National Cancer Institute's Common Terminology Criteria for Adverse Events (NCI-CTCAE) version 4.03 will be used to grade severity of adverse events (AEs).

Type of control	Not applicable
Data Monitoring Committee	Yes
Number of patients	A maximum of 30 patients will be enrolled

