6.3.1.2 Full screening failure

A patient who passes the prescreening, including the mesothelin overexpression testing, but for any other reason (e.g., failure to satisfy the remaining selection criteria) terminates the study before enrollment is regarded as a “full screening failure”. See Section 11.1 for data to be collected for screening failures.

Re-starting the defined set of screening procedures to enable the “screening failure” patient’s participation at a later time point is not allowed – with the following exceptions:

- The patient had successfully passed the screening procedures, but could not start subsequent treatment on schedule.
- Initial screening occurred too early to complete the required washout period after prior therapy.
- The in- / exclusion criteria preventing the patient’s initial attempt to participate have been changed (via protocol amendment).
- Equivocal screening results require further testing for clarification even if, for logistical reasons, the further testing cannot be performed within the allocated time window (e.g. equivocal laboratory creatinine clearance requiring formal creatinine clearance measurement).
- Resolution of toxicity, now meeting all criteria

In any case, the investigator has to ensure that the repeated screening procedures do not expose the patient to an unjustifiable health risk. Also, for re-screening, the patient has to resign the main consent document (for the full study), even if it was not changed after the patient’s previous screening.

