9.2.1 Prescreening

A prescreening step, including mesothelin expression level testing, can be performed without evidence of disease progression after the initial treatment at the investigator's discretion.

Written patient informed consent for prescreening must be obtained before any prescreening

or study-specific procedures. Enrollment in the study is defined as the signing of the consent form.

Written informed consent for prescreening.

Enroll patient in OnCore.

Demographics (see Section 9.3.1).

Study disease characteristics and prior therapies for the study indication (see Section 9.3.3).

Check eligibility criteria for prescreening (see Section 6.1.1).

Toxicity/AE assessment (see Section 9.5.1). At prescreening, only AEs and SAEs that are related to study-specific procedures are mandatory to be reported.

Concomitant medication review (see Section 8.1). At prescreening, only concomitant medications that are administered to treat AEs related to study-specific procedures are mandatory to be reported.

Mandatory biomarker archival or fresh biopsy tissue (see Section 9.6.1).

All patients enrolled into the study will be listed on a patient enrollment log maintained in OnCore.

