9.2.3 Treatment period

After all screening assessments have been completed and the patient's eligibility has been confirmed and documented (confirmation of mesothelin overexpression moderate [2+] and stronger [3+] in at least 30% of tumor cells will be obtained from central lab and confirmation of at least 1 measurable lesion present will be obtained from radiological review), the patient may begin treatment.

9.2.3.1 Treatment – Cycle 1

Cycle 1 Day 1

The following procedures should be performed on C1D1 **before receiving study treatment** unless otherwise specified in the protocol:

Check eligibility criteria for full study, and exclusion criteria (see Section 6.1.2 and 6.2, respectively).

Enroll patient on treatment in OnCore.

Toxicity/AE assessment (see Section 9.5.1).

Concomitant medication review (see Section 8.1).

Brief physical examination (see Section 9.5.3.2.2).

Vital signs (see Section 9.5.3.4).

Weight.

Height will be measured if it was not measured during the screening period.

ECOG PS assessment (see Section 9.5.3.3).

Laboratory (see Section 9.5.3.1):

- Complete blood count with differential.
- Electrolyte and chemistry panel (CMP).
- Urine dipstick.
- Serum CEA and CA19-9.

Biomarker plasma collection for soluble mesothelin (see Section 9.6.1).

Biomarker plasma collection for exploratory analysis (see Section 9.6.1).

Study treatment administration (IV infusion [see Section 7.3]).

12-lead ECG (see Section 9.5.3.5).

Ophthalmologic examination (Schirmer test only) (see Section 9.5.3.7). If the screening period Schirmer test is conducted within 7 days of starting study treatment, the test does not need to be repeated at C1D1.

Cycle 1 Day 8

For assessments of this visit, time windows of -1 day and +1 day are acceptable unless otherwise specified in the protocol.

The following procedures should be performed on C1D8 **before receiving study treatment** unless otherwise specified in the protocol:

Toxicity/AE assessment (see Section 9.5.1).

Concomitant medication review (see Section 8.1).

Brief physical examination (see Section 9.5.3.2.2).

Vital signs (see Section 9.5.3.4).

Weight.

Laboratory (see Section 9.5.3.1):

- Complete blood count with differential.
- Electrolyte and chemistry panel (CMP).

Cycle 1 Day 15

For assessments of this visit, time windows of -1 day and +1 day are acceptable unless otherwise specified in the protocol.

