10.2.2.1 Primary efficacy analysis

The primary efficacy analysis tests the following hypotheses:

H0: In patients with advanced or metastatic pancreatic cancer overexpressing mesothelin and pretreated with prior chemotherapy, a response per RECIST under treatment with anetumab ravtansine at 6.5 mg/kg Q3W would not be seen.

versus

HA: In patients with advanced or metastatic pancreatic cancer overexpressing mesothelin and pretreated with prior chemotherapy, a response per RECIST under treatment with anetumab ravtansine at 6.5 mg/kg Q3W would be seen.

The minimax, Simon 2-stage design testing 5% null hypothesis versus a 21% alternative requires a maximum of 30 patients. If there are no patients exhibiting any response among the first 20 then the trial will terminate early. If there is at least one response among the first 20 then the trial will accrue an additional 10 patients for a maximum of 30. Four or more responses out of 30 will reject the null hypothesis in favor of the 21% response alternative. These criteria have significance level (alpha) 0.1 and power 90%. The probability of stopping early is 36% if the response rate is 5% or lower. The expected sample size is 26.4.

Sensitivity analyses will be performed, including analyses to assess the impact of missing data and the possibility of survivorship and selection biases. Further details will be described in the SAP.

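### Do the words evaluable (10.3) and enrollment (9.2.1) leave the two-stage rule without a fixed set of patients to count?

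*Combined protocol and SAP*

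**What the plan says.** The decision rule appears in the Synopsis, 5.1 and 10.2.2.1, each time with the same unit. In 10.2.2.1 it reads "If there are no patients exhibiting any response among the first 20 then the trial will terminate early"; otherwise 10 more patients are accrued, and four or more responses out of 30 reject the 5% null hypothesis.

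On the analysis set, 5.1 states that "all patients treated with at least one dose of Anetumab will be included", and the Synopsis agrees. Section 6.3.5 allows no replacement.

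On timing, 10.3 consists of one sentence: "An interim analysis for RR at the time 20 patients are evaluable will be performed". Elsewhere the word evaluable describes a baseline scan (9.2.2, 9.4.1) or non-target lesions (Appendix 16.3), never a class of patients.

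On the cap, the Synopsis and 5.1 say "A maximum of 30 patients will be enrolled in a minimax, Simon 2-stage design". Section 9.2.1, which concerns prescreening, says "Enrollment in the study is defined as the signing of the consent form". Section 6.3.1.2 places enrollment later: someone who passes prescreening but "terminates the study before enrollment is regarded as a" full screening failure has already signed consent. Section 9.2.3.1 has a separate step on Cycle 1 Day 1, before the first dose: "Enroll patient on treatment in OnCore".

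**The concern.** A two-stage design has its stated properties only if the 20 and the 30 are counted on one set of patients. Here three labels are in use (first 20, evaluable, enrolled), and one has no definition for patients.

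Two consequences seem possible. First, if some treated patients never become evaluable, waiting for 20 evaluable patients means that more than 20 have been treated when futility is judged. Two analysts might then choose different sets of 20, and the stated stopping probability of 36% and expected sample size of 26.4 might no longer apply. Second, if the cap of 30 counts consent signatures, every screening failure uses up a place. Fewer than 30 patients would be treated, and power would fall below the stated 90%.

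**Working it through.** **1. The plan's own figures.** Inputs from 10.2.2.1: null rate 0.05, alternative 0.21, stop on 0 responses in 20, reject on 4 or more in 30. Let p be the response rate.

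- Early stopping = (1 − p)^20. At 5%: 0.95^20 = 0.3585. At 21%: 0.79^20 = 0.0090.
- Expected N at 5% = 20 × 0.3585 + 30 × 0.6415 = 26.4.
- P(reject) = P(at least 4 of 30) − P(0 of 20) × P(at least 4 of 10).
  - At 5%: 0.0608 − 0.3585 × 0.0010 = 0.0604.
  - At 21%: 0.9016 − 0.0090 × 0.1391 = 0.9003.

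The 36%, the 26.4 and the 90% all reproduce when 20 and then 30 treated patients are counted. The stated alpha of 0.1 is the design ceiling; the attained value is 0.060.

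**2. Evaluable as a timing trigger; the first 20 treated decide.** If m patients have been treated by the look, early stopping stays at 0.3585 because the same 20 decide. Alpha and power stay at 0.0604 and 0.9003. Only the expected N moves:

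E[N] at 5% = m × 0.3585 + 30 × 0.6415, so each extra patient adds 0.36.

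The documents give no non-evaluable rate. Assuming 10% to 25%, 20/0.90 = 22.2 and 20/0.75 = 26.7, so m is about 22 to 27:

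| m | E[N] at 5% |
|---|---|
| 20 | 26.4 |
| 22 | 27.1 |
| 25 | 28.2 |
| 27 | 28.9 |

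**3. Accrual not held during the wait.** The documents give no accrual rate. Assume 1 to 3 patients per month and a wait of 6 weeks (first scan) to 12 weeks (about the time needed if a response must be confirmed, as 9.4.1 asks). With 52/12 = 4.33 weeks per month:

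- Low end: 1 × 6/4.33 = 1.4 extra patients; E[N] = 26.4 + 0.3585 × 1.4 = 26.9.
- High end: 3 × 12/4.33 = 8.3 extra patients; E[N] = 26.4 + 0.3585 × 8.3 = 29.4.

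**4. A stricter reading: stop only if nobody treated by the look has responded.** No section says this, but it bounds the effect.

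| m | Early stopping at 5% | E[N] at 5% | Alpha | Power |
|---|---|---|---|---|
| 22 | 0.95^22 = 0.324 | 27.4 | 0.0607 | 0.901 |
| 27 | 0.95^27 = 0.250 | 29.2 | 0.0608 | 0.902 |

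Even here alpha stays below 0.10 and power above 0.90.

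**5. A cap on consent signatures.** With the same rejection rule, power is 0.885 if 29 patients are treated and 0.848 if 27 are. This reading does not fit the rest of the protocol. Section 5.1 says "All patients will be treated with an anti-mesothelin immuno-conjugate" of the same 30, the rejection rule has 30 as its denominator, and 9.2.3.1 records enrollment on treatment as a step separate from the OnCore entry at prescreening.

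**The case for a change.** The best case for a change is that a futility rule should leave nothing to interpretation before the look. Section 10.3 does not itself defer to a later SAP, no definition of an evaluable patient appears in the documents supplied, and the fix is a few words. Stopping at 20 saves 30 − 26.4 = 3.6 patients on average at a 5% response rate. If 27 were treated before the decision, the saving would shrink to 30 − 28.9 = 1.1, and more patients would receive a drug that does not work.

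Part of this stands. The word is undefined, and 9.2.1 and 6.3.1.2 do disagree on when enrollment occurs. Section 10.3 also leaves open whether the look uses the first scan or a confirmed response. But these are gaps of detail. Section 10.3 restates no rule and gives no denominator, so it does not compete with the unit used wherever the rule is stated. Section 10.2.2.1 is also sequential: the second 10 are accrued after a response has been seen among the first 20, so treating many patients during the wait is not what the plan describes.

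A second argument is that counting unscanned patients as non-responders costs power: 0.844 with 10% non-evaluable and 0.715 with 25%. Those figures arise only if 21% is the rate among evaluable patients and evaluability is unrelated to response. Section 3.2 states the 21% target as a share of treated patients, so the loss does not apply. It would in any case come from the treated-patient denominator, not from the wording of 10.3.

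**Conclusion.** The concern does not call for a change. An analyst following the plan would take the first 20 dosed patients, wait until their response can be judged, and continue to 30 dosed patients if any has responded. That gives the stated design. The remaining uncertainty is in the expected sample size when the drug is inactive: 26.4 if accrual stops at 20, and 26.9 to 29.4 under the assumed rates (10% to 25% non-evaluable, or 1 to 3 patients per month over a wait of 6 to 12 weeks). The maximum of 30, the error rates and the final test are unaffected. The enrollment mismatch between 9.2.1 and 6.3.1.2 is a clerical slip: the only reading on which it costs power is excluded by the surrounding text. These conclusions rest on 21% being a rate per treated patient, as 3.2 has it, and on the first 20 being counted in order of treatment.
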